3.2 Secondary Objective(s) & Hypothesis(es)

Key Secondary Objectives (* centrally confirmed):

1. **Objective:** To estimate the Duration of Response (DOR) to pembrolizumab as 2L+ monotherapy for PD-L1 (+) mTNBC* (**Cohort A**), mTNBC* independent of PD-L1 status (**Cohort A**), and PD-L1 strong (+) mTNBC* (**Cohorts A+C**), based on RECIST 1.1 as assessed by the central imaging vendor.
2. **Objective:** To estimate the Disease Control Rate (DCR), Progression-Free Survival (PFS) and Overall Survival (OS) in patients receiving pembrolizumab as 2L+ monotherapy for PD-L1 (+) mTNBC* (**Cohort A**), mTNBC* independent of PD-L1 status (**Cohort A**), and PD-L1 strong (+) mTNBC* (**Cohorts A+C**), based on RECIST 1.1 as assessed by the central imaging vendor.

Other (non-key) Secondary Objectives (* centrally confirmed):

1. **Objective (Cohort B):** To estimate the antitumor efficacy (as measured by ORR, DOR, DCR, PFS, and OS) of pembrolizumab as 1L monotherapy for PD-L1 (+) mTNBC*, based on RECIST 1.1 as assessed by the central imaging vendor.
2. **Objective (Cohort A):** To explore the association between PD-L1 protein expression by IHC and antitumor efficacy of pembrolizumab in 2L+ monotherapy mTNBC based on RECIST 1.1 as assessed by the central imaging vendor.

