7.1.2.6.2 On Study Tumor Imaging

The first post treatment tumor imaging assessment should be performed at 9 weeks (63 days \pm 7 days) from the date of allocation. Thereafter, subsequent tumor imaging should be performed every 9 weeks (63 days \pm 7 days) or more frequently, if clinically indicated. After 12 months, imaging frequency should be reduced to every 12 weeks (84 \pm 7 days). Imaging should follow calendar days and not be delayed for any dose interruptions that may occur.

Per RECIST 1.1, partial or complete response should be confirmed by a repeat tumor imaging not less than 4 weeks from the date the response was first documented. The tumor imaging for confirmation of response may be performed at the earliest 4 weeks after the first indication of response, or at the next scheduled tumor imaging, whichever is clinically indicated.

Imaging should continue to be performed until disease progression, the start of new anti-cancer treatment, withdrawal of consent, death, or notification by the SPONSOR, whichever occurs first. Disease progression may be confirmed at least 4 weeks after the first tumor imaging indicating progressive disease in clinically stable subjects.

Subjects who have unconfirmed disease progression may continue on treatment until progression is confirmed (or possibly even later) provided they have met the conditions detailed in Section 7.1.2.6.5.

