8.1 Statistical Analysis Plan Summary

This section contains a brief summary of the statistical analyses for this trial. Full detail is in the Statistical Analysis Plan (SAP) (Section 8.2).

In addition, a separate analysis plan document will be issued prior to biomarker unblinding for each of the following laboratory procedures and assessments: (1) Biomarkers (detailed in Section 7.1.3.4 and 7.1.3.5) and their association with antitumor efficacy and (2) Pharmacokinetic and pharmacodynamics evaluation (detailed in Section 7.1.3.3)

Study Design Overview	A Phase II Clinical Trial of Pembrolizumab as Monotherapy in Subjects with Metastatic Triple-Negative Breast Cancer (mTNBC)
Treatment Assignment	Treatment assignment is open label.
Analysis Populations	Efficacy: All Subjects as Treated (ASaT) Safety: All Subjects as Treated (ASaT)
Primary Endpoint(s)	Objective Response Rate (ORR)
Statistical Methods for Key	ORR estimation

Efficacy Analyses	
 • 2L+ population 
 ○ PD-L1 (+) population (Cohort A) ○ Overall population (Cohort A) ○ PD-L1 strong (+) population (Cohorts A+C) • 1L population (Cohort B) • Counts and percentages • 95% Agresti-Coull confidence intervals
Statistical Methods for Key Safety Analyses	Counts and percentages of AEs will be provided. Confidence intervals for rates of AEs of clinical interest will be computed using the exact binomial method.
Interim Analyses	
 • Futility analysis for 2L+ subjects (Cohort A) with PD-L1 (-) tumors based on no progression 
 ○ ~25 PD-L1 (-) subjects ○ If no response or stable disease, continue 2L+ population (Cohort A) in PD-L1 (+) patients only • Evaluation of expansion to Cohort C for PD-L1 strong (+) population based on ORR. 
 ○ ~10 patients evaluable through response, progression or 18-week scan, whichever comes first. ○ Cohort C may start if ≥ 1 responses observed 
The final analysis of Cohorts A and C combined is to be completed when subjects are evaluable through response, progression or 18-week scan, whichever comes first.

Multiplicity	This is an estimation study. No multiplicity adjustment will be applied.

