8.2 Statistical Analysis Plan

8.2.1 Responsibility for Analyses/In-House Blinding

The statistical analysis of the data obtained from this study will be the responsibility of the clinical biostatistics department of the SPONSOR.

This trial is being conducted as an open-label non-randomized single-arm clinical trial for each cohort, i.e., subjects, investigators, and SPONSOR personnel will be aware of subject treatment assignments after each subject is enrolled and treatment is assigned. The investigator and the study team at the Sponsor consisting of clinical, statistical, statistical programming and data management personnel, will be blinded to subject-level PD-L1 biomarker results in Cohort A. A designated Sponsor team (may include unblinded Sponsor

statisticians, unblinded Sponsor statistical programmers, unblinded Sponsor clinical scientists, unblinded clinical directors, and unblinded data management personnel) will have access to the subject-level PD-L1 results for the purpose of data review and will have no other responsibilities associated with the study. A summary of PD-L1 biomarker prevalence and biomarker cutoff analysis will be provided to the study team at the Sponsor by the unblinded Sponsor statistician. Biomarker cutoff analysis will inform the team about the outcome of the interim analyses and whether or not the pre-specified go/no go decision criteria are met. The estimation of tumor efficacy, e.g., ORR, DOR and DCR, etc. based on RECIST 1.1 by the central imaging vendor may be provided by the unblinded statistician while the trial is ongoing.

The Clinical Biostatistics department will generate the allocation schedule for study treatment assignment. Allocation will be implemented in an interactive voice response system (IVRS).

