8.2.3.1 Efficacy Endpoints

The primary efficacy endpoint is objective response rate (ORR), defined as the proportion of subjects in the analysis population who have complete response (CR) or partial response (PR), based on RECIST 1.1 by the central imaging vendor at any time during the study. As supportive analyses, ORR will also be evaluated by a) site investigator and local radiology review based on RECIST 1.1 and b) irRECIST by the central imaging vendor.

Secondary efficacy endpoints include:

- Duration of response (DOR), defined as the time from first documented evidence of CR or PR until disease progression or death due to any cause, whichever occurs first, for subjects who demonstrate CR or PR, based on RECIST 1.1 by the central imaging vendor.
- Disease control rate (DCR), defined as the percentage of subjects who have achieved confirmed CR or PR or have demonstrated SD for at least 24 weeks prior to any evidence of progression, based on RECIST 1.1 by the central imaging vendor.
- Progression-free survival (PFS), defined as the time from first dose of study medication to the first documented disease progression or death due to any cause, whichever comes first, based on RECIST 1.1 by the central imaging vendor.

- Overall survival (OS), defined as the time from first dose of study medication to death due to any cause.

As exploratory endpoints, DOR and DCR and PFS will also be evaluated based on a) RECIST 1.1 by study site and local radiology review and b) irRECIST by the central imaging vendor.

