8.2.5 Statistical Methods

8.2.5.1 Statistical Methods for Efficacy Analyses

Efficacy of pembrolizumab as 2L+ monotherapy for mTNBC will be evaluated primarily in PD-L1 (+) and overall population (all comers) in Cohort A, and also in subjects with PD-L1 strong (+) tumors from Cohorts A and C combined. Cohort A will be evaluated for association between PD-L1 biomarker expression and antitumor activity. A separate biomarker SAP will be devoted to association between PD-L1 biomarker expression and antitumor activity analysis.

The primary efficacy endpoints are ORR based on RECIST 1.1 by the central imaging vendor in subjects with PD-L1 (+) mTNBC of Cohorts A, overall population (all comers) of Cohort A and in subjects with PD-L1 strong (+) mTNBC. The point estimate 95% Agresti-Coull (A-C) confidence interval (CI) (as determined by the upper and lower 97.5% one-sided confidence bounds) will be provided based on normal approximation for the binomial distribution. Subjects without response data will be counted as non-responders.

Similarly, a supportive analysis to the primary method, ORR based on RECIST 1.1 by study site investigator and local radiology review will also be performed in the same fashion.

For the secondary endpoint of DCR, similar estimation methods used for ORR will be applied.

For DOR, PFS and OS, Kaplan-Meier (KM) curves, median estimates, and survival at 6 and 12 months based on the KM curves (95% CI is based on Greenwood's formula) will be provided as appropriate. Subjects without efficacy evaluation data or without survival data will be censored at Day 1. The restricted mean survival time (RMST) for DOR will also be provided as a supportive analysis.

Censoring rules for DOR are summarized in [Table 9](#).

Table 9 Censoring Rules for DOR

Situation	Date of progression or censoring	Outcome
No progression nor death, no new anti-cancer therapy initiated	Last adequate assessment	Censor (non-event)
No progression nor death, new anti-cancer therapy initiated	Last adequate assessment before new anti-cancer therapy initiated	Censor (non-event)
≥ 2 consecutive missed adequate disease assessments	Last adequate assessment prior to ≥ 2 missed adequate disease assessments	Censor (non-event)
Death or progression after ≤ 1 missed adequate disease assessments	Death or progression	End of response (Event)

A missed disease assessment includes any assessment that is not obtained or is considered inadequate for evaluation of response.

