Similar estimation methods will be applied to the efficacy analyses for the subjects with PD-L1 (+) mTNBC in Cohort B.

[Table 10](#) summarizes the key efficacy analyses for primary and secondary endpoints in this study.

Table 10 Analysis Strategy for Primary/Secondary Efficacy Endpoints in Cohorts A and C

Endpoint/Variable (Description, Time Point)	Statistical Method	Analysis Population	Missing Data Approach
Primary:			
ORR, based on RECIST1.1 by the central imaging vendor	95% Agresti-Coull CI	ASaT - PD-L1 (+) - overall - PD-L1 strong (+)	Subjects with missing data are considered non-responders
Secondary:			
Response duration (DOR) Based on RECIST1.1 
 o by the central imaging vendor o by study site investigator and local radiology review 	Summary statistics using Kaplan-Meier method	All responders - PD-L1 (+) - overall - PD-L1 strong (+)	Non-responders are excluded in analysis
ORR Based on RECIST1.1 
 o by study site investigator and local radiology review 	Agresti-Coull 95% CI	ASaT - PD-L1 (+) - overall - PD-L1 strong (+)	Subjects with missing data are considered non-responders
DCR Based on RECIST1.1 
 o by the central imaging vendor o by study site investigator and local radiology review 	Agresti-Coull 95% CI	ASaT - PD-L1 (+) - overall - PD-L1 strong (+)	Subjects with missing data are considered non-responders
Progression-free survival (PFS) Based on RECIST1.1 
 o by the central imaging vendor o by study site investigator and local radiology review 	Summary statistics using Kaplan-Meier method	ASaT - PD-L1 (+) - overall - PD-L1 strong (+)	Censored at last assessment
Overall survival (OS)	Summary statistics using Kaplan-Meier method	ASaT - PD-L1 (+) - overall - PD-L1 strong (+)	Censored at last assessment
95% confidence interval is determined by the upper and lower 97.5% one-sided confidence bounds.			

Similar efficacy methods will be applied to Cohort B for subjects with PD-L1 (+) tumors receiving pembrolizumab as 1L monotherapy for mTNBC.

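### If Cohorts A+C are cut at the 18-week trigger, the PD-L1 strong (+) disease control rate can be slightly understated, because its stable-disease criterion needs 24 weeks

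*Combined protocol and SAP*

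**What the plan says.** **Timing.** The Interim Analyses row of the summary table in protocol 8.1, repeated in sSAP 3.1, states: "The final analysis of Cohorts A and C combined is to be completed when subjects are evaluable through response, progression or 18-week scan", taking the earliest of these.

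**Endpoint.** Protocol 8.2.3.1 and sSAP 3.4.1 define DCR as the percentage of subjects with "confirmed CR or PR or have demonstrated SD for at least 24 weeks prior to any evidence of progression", by central RECIST 1.1. Protocol 3.2 lists DCR in PD-L1 strong (+) disease (Cohorts A+C) among the key secondary objectives.

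**Estimation.** Protocol 8.2.5.1 says: "For the secondary endpoint of DCR, similar estimation methods used for ORR will be applied". DCR is therefore a simple proportion of the All-Subjects-as-Treated (ASaT) population with an Agresti-Coull interval. Table 10 adds, for DCR: "Subjects with missing data are considered non-responders". The ASaT definition in 8.2.4.1 has no minimum follow-up.

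**Scans.** Protocol 7.1.2.6.2 puts the first on-study scan at week 9 from allocation. "Thereafter, subsequent tumor imaging should be performed every 9 weeks", so year-1 scans fall at weeks 9, 18, 27 and so on, each within 7 days.

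**Enrolment order.** Under protocol 2.1, Cohort C opens only once Cohort A is full. Protocol 8.2.7 expects about 45 subjects in Cohort C and about 55 strong (+) subjects in total.

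**The concern.** The trigger is shorter than the period over which one component of DCR is defined. A scan at week 18 (week 19 at the latest) cannot show 24 weeks of SD; the first scheduled scan that can is at week 27. At a cut made on the trigger, a recently enrolled subject in ongoing SD does not meet the definition. Whether that subject is classed as observed or as missing, the result is a failure in an uncensored proportion. More follow-up could move the subject to disease control but never the other way, so the error has one direction.

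It falls on the A+C strong (+) estimate because the late entrants are Cohort C subjects, who make up most of that population. The estimate is single-arm, so no comparator shares the error. At stake is the accuracy of one descriptive key secondary figure.

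**Working it through.** **1. The plan's own figure.** DCR inherits the ORR method, so the Table 13 row for 11/55 was checked first. With z² = 3.84: n~ = 55 + 3.84 = 58.84; p~ = (11 + 1.92)/58.84 = 0.2196; half-width = 1.96 × √(0.2196 × 0.7804/58.84) = 0.106. The interval is 11.4% to 32.5%, as printed.

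**2. The gap.** Trigger to criterion: 24 − 18 = 6 weeks. Trigger to the next scheduled scan: 27 − 18 = 9 weeks. Subjects allocated earlier than that already have their week-27 scan at the cut.

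**3. Effect per subject.** 1/55 = 1.8 points. In Table 13, for example, a mature 14/55 is 25.5% (15.7, 38.4); with one subject cut early it becomes 13/55, or 23.6% (14.2, 36.5).

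**4. Share who would reach 24 weeks of SD (assumption).** The documents give no figure. Section 4.2.1 offers two anchors: 25.9% SD on 8-weekly scans in the earlier phase Ib study, and a median PFS of 2–3 months in previously treated disease. Assuming exponential PFS, the share of those in SD at week 8 who are progression-free at week 24 is 0.5^(16/median):
- median 2 months = 8.70 weeks: 0.5^(16/8.70) = 0.279; × 0.259 = 7.2%
- median 3 months = 13.04 weeks: 0.5^(16/13.04) = 0.427; × 0.259 = 11.1%

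**5. Late entrants and expected shortfall.** Accrual time is also not given. Assuming uniform accrual of 45 Cohort C subjects over T weeks, late entrants = 45 × 9/T. The shortfall is late entrants × share / 55.

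| T (weeks) | Late entrants | Missed (7.2–11.1%) | Shortfall (points) |
|---|---|---|---|
| 26 | 15.6 | 1.1–1.7 | 2.1–3.1 |
| 52 | 7.8 | 0.56–0.86 | 1.0–1.6 |
| 78 | 5.2 | 0.38–0.57 | 0.7–1.0 |
| 104 | 3.9 | 0.28–0.43 | 0.5–0.8 |

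With the 6-week window each figure is two-thirds as large, for example 0.7–1.0 points at 52 weeks.

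**6. Which accrual time is plausible.** Protocol 2.1 and 8.2.7 imply 10–15 strong (+) subjects among about 160, that is 10/160 = 6% to 15/160 = 9%. Finding 40–45 more means testing about 40/0.094 = 427 to 45/0.0625 = 720 otherwise eligible patients. Over 26 weeks that is 16–28 a week, a rate at which all 160 subjects of Cohort A would be found in about 6–10 weeks. The 26-week row therefore fits the plan's own figures poorly.

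**The case against.** The strongest reply is that the sentence was never meant as the data cut for every endpoint. It stands in a summary row about interim analyses, the only efficacy endpoint named in that table is ORR, and nearly the same phrase defines readiness for the second interim analysis, which is about response. Section 8.2, where the full detail is said to lie, does not repeat it as a final trigger. Other text points to longer follow-up: 6- and 12-month Kaplan-Meier estimates, imaging until progression or end of study, survival updates before database locks, and a 30–36 month trial. This stands in part: the harm is conditional on cutting at the trigger. But the Kaplan-Meier estimates cover only DOR, PFS and OS, and none of the other passages fixes a DCR cut. Section 8.2.1 says "The estimation of tumor efficacy, e.g., ORR, DOR and DCR, etc. based on RECIST 1.1 by the central imaging vendor may be provided" while the trial is ongoing, again without a date.

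The second reply is that the effect is small and conservative, in an estimation study. That stands in full.

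A third question is whether a later cut must also wait for confirmatory scans, since 7.1.2.6.2 says "partial or complete response should be confirmed by a repeat tumor imaging not less than 4 weeks from the date the response was first documented". It need not. A subject whose first response appears at week 27 has gone more than 24 weeks without progression and already qualifies through the SD arm.

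**Conclusion.** The point holds in conditional form and is minor. If A+C data are cut at the stated trigger, the strong (+) DCR can be understated and cannot be overstated. With 7–11% reaching 24 weeks of SD and a 9-week window, the expected shortfall is about 1.0–1.6 points at 52-week accrual and 0.5–1.0 points at 78–104 weeks, about one subject or fewer. The interval at 14/55 in Table 13 is 22.7 points wide (38.4 − 15.7). The share reaching 24 weeks, the exponential form and the accrual time are assumptions; the true effect could be zero.

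Three stronger readings are not supported:
- A reader might infer a shortfall of 3 points or more. That needs Cohort C to accrue in about 26 weeks, at odds with the implied 6–9% prevalence; going beyond about 3 points also needs a larger long-SD share than the anchors give.
- A reader might extend the point to Cohort B or Cohort A alone. The documents state no final-analysis trigger for either.
- A reader might see a threat to the primary result or to a decision. ORR does not use the 24-week criterion; DOR, PFS and OS are handled by censoring; and no hypothesis or go/no-go rule uses DCR.

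**What to change.** In protocol 8.1 and sSAP 3.1, keep the 18-week trigger for the ORR read. Add that DCR for Cohorts A+C is reported at a data cut no earlier than the last treated subject's week-27 scan, or that subject's earlier progression, death or withdrawal. If DCR is also shown at the 18-week cut, label it preliminary and give the number of subjects in ongoing SD with less than 24 weeks of follow-up.

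Cost: the A+C DCR arrives about 9 weeks later (27 − 18). ORR is not delayed and the scans are already scheduled. Because 8.1 is part of the protocol, the change needs protocol text as well as sSAP text.

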8.2 Statistical Analysis Plan

8.2.1 Responsibility for Analyses/In-House Blinding

The statistical analysis of the data obtained from this study will be the responsibility of the clinical biostatistics department of the SPONSOR.

This trial is being conducted as an open-label non-randomized single-arm clinical trial for each cohort, i.e., subjects, investigators, and SPONSOR personnel will be aware of subject treatment assignments after each subject is enrolled and treatment is assigned. The investigator and the study team at the Sponsor consisting of clinical, statistical, statistical programming and data management personnel, will be blinded to subject-level PD-L1 biomarker results in Cohort A. A designated Sponsor team (may include unblinded Sponsor

statisticians, unblinded Sponsor statistical programmers, unblinded Sponsor clinical scientists, unblinded clinical directors, and unblinded data management personnel) will have access to the subject-level PD-L1 results for the purpose of data review and will have no other responsibilities associated with the study. A summary of PD-L1 biomarker prevalence and biomarker cutoff analysis will be provided to the study team at the Sponsor by the unblinded Sponsor statistician. Biomarker cutoff analysis will inform the team about the outcome of the interim analyses and whether or not the pre-specified go/no go decision criteria are met. The estimation of tumor efficacy, e.g., ORR, DOR and DCR, etc. based on RECIST 1.1 by the central imaging vendor may be provided by the unblinded statistician while the trial is ongoing.

The Clinical Biostatistics department will generate the allocation schedule for study treatment assignment. Allocation will be implemented in an interactive voice response system (IVRS).

8.2.2 Hypotheses/Estimation

This is an estimation study. Objectives of the study are stated in Section 3.0.

8.2.3 Analysis Endpoints

The efficacy and safety endpoints that will be evaluated are listed below, followed by the descriptions of the derivations of selected endpoints.

8.2.3.1 Efficacy Endpoints

The primary efficacy endpoint is objective response rate (ORR), defined as the proportion of subjects in the analysis population who have complete response (CR) or partial response (PR), based on RECIST 1.1 by the central imaging vendor at any time during the study. As supportive analyses, ORR will also be evaluated by a) site investigator and local radiology review based on RECIST 1.1 and b) irRECIST by the central imaging vendor.

Secondary efficacy endpoints include:

- Duration of response (DOR), defined as the time from first documented evidence of CR or PR until disease progression or death due to any cause, whichever occurs first, for subjects who demonstrate CR or PR, based on RECIST 1.1 by the central imaging vendor.
- Disease control rate (DCR), defined as the percentage of subjects who have achieved confirmed CR or PR or have demonstrated SD for at least 24 weeks prior to any evidence of progression, based on RECIST 1.1 by the central imaging vendor.
- Progression-free survival (PFS), defined as the time from first dose of study medication to the first documented disease progression or death due to any cause, whichever comes first, based on RECIST 1.1 by the central imaging vendor.

- Overall survival (OS), defined as the time from first dose of study medication to death due to any cause.

As exploratory endpoints, DOR and DCR and PFS will also be evaluated based on a) RECIST 1.1 by study site and local radiology review and b) irRECIST by the central imaging vendor.

